4.1 Primary Objective

- To determine the onset of action of Mavenclad® in subjects with highly active relapsing multiple sclerosis (RMS).

4.1.1 Primary Endpoint(s)

- Differences in the counts of CUA MRI lesions during the first 6 months (i.e. during periods months 16, 26, 36) compared to baseline (i.e. the period screening to baseline)

4.2 Secondary Objective

- To assess the effect of Mavenclad® on different immune system composites in particular cell subtypes count and repopulation

4.2.1 Secondary Endpoints

- Characterization of immune cell subsets count at the end of 3, 6, 12, 15, 18 and 24 months compared to baseline

4.3 Tertiary Objectives

- To assess the safety and tolerability of Mavenclad®
- To assess the effect of Mavenclad® on progression of disability, cognition and incidence of relapse

- CCI [REDACTED]

4.3.1 Tertiary Endpoints

Safety:

- Occurrences of treatment-emergent adverse events (TEAEs) and serious adverse events (SAEs) including and up to 24 months

Clinical:

- Changes in Symbol Digit Modality Test (SDMT) outcome at the end of 6, 12, 18 and 24 months compared to baseline
- Disability evolution as measured by EDSS/KFS, 9-Hole Peg Test (9HPT), Timed 25-Foot Walk (T25FW) at the end of 6, 12, 18 and 24 months compared to baseline
- ARR between baseline and 24 months
- Changes in CUA lesions during the following post-baseline periods compared to baseline period (i.e. the period from screening to baseline):
 - Period of month 6 to month 12
 - Period of month 1 to month 12
 - Period of month 18 to month 24
 - Period of month 1 to month 24

Further periods and comparisons may be defined in the SAP

- Number of CUA lesions during the baseline and post-baseline periods
- Changes in active T1 Gd+ lesion count at the end of 1, 2, 3, 6, 12, 15, 18 and 24 months compared to baseline
- Volume changes of T1 Gd+ lesions at the end of 1, 2, 3, 6, 12, 15, 18 and 24 months compared to baseline
- Number of T1 hypointense lesions at the end of 1, 2, 3, 6, 12, 15, 18 and 24 months compared to baseline
- Change in volume of T1 hypointense lesions at the end of 1, 2, 3, 6, 12, 15, 18 and 24 months compared to baseline
- Changes in new T2 lesion count during the post-baseline periods compared to the baseline period as defined above
- Responder rate during the different periods as defined above with responder being defined as subjects with a CUA lesion count reduction of at least 1
- Changes in T2 lesion volume at the end of 12 and 24 months compared to baseline
- Changes in Magnetization Transfer Ratio (MTR) at the end of 1, 2, 3, 6, 12, 15, 18 and 24 months compared to baseline
- Changes in brain volume at the end of 1, 2, 3, 6, 12 and 24 months compared to baseline (and changes at 24 months compared to 6 months to exclude pseudo-atrophy)
- No Evidence of Disease Activity (NEDA) at 24 months
- No Evidence of Progression or Active Disease (NEPAD) at 24 months

CCI [REDACTED]

[figure not shown]

5 Investigational Plan

5.1 Overall Trial Design and Plan

A schematic of the trial design is presented in Figure 1.

Figure 1 Schematic of the Trial Design

Abbreviations: 9HPT=9-hole peg test; CUA=combined unique active; EDSS=expanded disability status scale; KFS=Kurtzke Functional System; HIV=human immunodeficiency virus; MRI=magnetic resonance imaging; SDMT=symbol digit modalities test; T25FW=timed 25-foot walk; TB=tuberculosis

A detailed schedule of trial procedures/assessments is provided in [Appendix 1: Schedule of Assessments](#).

5.2 Discussion of Trial Design

This will be an open-label, single-arm, multicenter, 2-year Phase IV trial. This trial will include a pre-Baseline screening period up to -3 months prior to drug administration, followed by an initial treatment course in Year 1 and a retreatment course in Year 2. Baseline is defined as the day on which the first dose of Mavenclad[®] is administered. Subjects will attend visits for assessments at the end of Months 1, 2, 3, 6, and 12 following Baseline and at the end of Month 15, 18, 24 following second treatment course (Month 1 of Year 2), respectively. Subjects will attend visits for blood sample as per mandatory monitoring at pre-Baseline and at Months 2, 6, 12, 14, 18 and 24.

Re-screening will be allowed once for those subjects who do not meet the inclusion/exclusion criteria within the above specified time limits. The Medical Monitor must promptly inform the Sponsor about requests and reasons for re-screening.

Subjects with RMS will receive Mavenclad[®] 3.5 mg/kg body weight over 2 years, administered as 1 treatment course of 1.75 mg/kg per year. Each treatment course will consist of 2 treatment weeks, one at the beginning of the first month and one at the beginning of the second month of the respective year. Each treatment week consists of 4 or 5 days on which a subject receives 10 mg or 20 mg (one or 2 tablets) as a single daily dose, depending on body weight as noted in SmPC (see [Appendix 13: Mavenclad Posology](#)).

MRI scans including lesion count, lesion volume, brain atrophy and MTR will be performed at screening, Baseline, and the end of Months 1, 2, 3, 6, 12, 15, 18, and 24. There will be a gap of at least 4 weeks between MRIs performed at screening and Baseline. Neurological examinations including EDSS/KFS, 9HPT, and T25FW will be performed at screening, Baseline, and the end of Months 6, 12, 18 and 24. SDMT will be performed at Baseline, and the end of Months 6, 12, 18 and 24. Blood specimens for immune cell subtypes count will be collected at Baseline, and the end of Months 3, 6, 12, 15, 18, 24. Physical examination including recording of vital signs will be performed at screening, Baseline, and Months 6, 12, 18 and 24. Safety laboratory tests including lymphocyte count, Hepatitis B and C, active and latent TB, HIV and urine/serum pregnancy test will be carried out at screening and before initiating second treatment course at Month 12; lymphocyte count will also be checked at 2 and 6 months after each treatment. If the absolute lymphocyte count at screening is done more than 4 weeks prior to Baseline, it should be repeated within 4 weeks of Baseline.

Subjects who discontinue Mavenclad[®] at any time during the trial will continue to participate in the scheduled visit for assessments. In the event of early discontinuation from the trial, the subject should return for the Early Termination visit for final assessment.

Following a relapse, subject may receive treatment with either acute short-term systemic corticosteroids or ACTH or plasma exchange at the discretion of the Investigator, following local good medical practice and international guidelines. A subject receiving any rescue medication with any other DMD will be followed-up by the investigator as standard of routine practise and will not participate further in any trial assessments; the subject should however complete the early termination visit for final assessment.

If a subject prematurely withdraws from the trial at any time, he/she will undergo all tests requested at the Early Termination visit as soon as possible.

Visit schedules for efficacy and safety assessments are detailed in [Appendix 1: Schedule of Assessments](#).

CCI [REDACTED]

5.2.1 Inclusion of Special Populations

Not applicable.

5.2.2 Steering Committee

A Steering Committee (SC) has been established; the Steering Committee Charter will be in place that describes the SC responsibilities.

The SC is a multidisciplinary group of lead trial investigators, medical experts, and Sponsor's personnel who, collectively, have the scientific, medical, and clinical trial management experience to design, conduct and evaluate the trial.

The SC provides advice and recommendations with regard to the design, the conduct, and the evaluation of the trial.

The SC is responsible for safeguarding the interests of participating subjects and for the conduct of the trial.

5.3 Selection of Trial Population

Only subjects meeting all inclusion criteria and no exclusion criteria will be enrolled into the trial as subjects. Prior to performing any trial assessments not part of the subject's routine medical care, the Investigator will ensure that the subject has provided written informed consent following the procedure described in Section 9.2.

5.3.1 Inclusion Criteria

To be eligible for inclusion into this study, the subjects must fulfill all of the following criteria:

1. Subjects must voluntarily give written informed consent. Subjects must read and fully understand the Informed Consent Form (ICF) and the requirements of the trial and must be willing to comply with all trial visits and assessments
2. Male or female subjects ≥ 18 years old
3. Highly active relapsing MS as defined by:
 - One relapse in the previous year and at least 1 T1 Gd+ lesion or 9 or more T2 lesions, while on therapy with other DMDs.
 - Two or more relapses in the previous year, whether on DMD treatment or not
4. EDSS score ≤ 5.0
5. Female subjects of child-bearing potential must use highly effective methods of contraception to prevent pregnancy for 4 weeks before initiation of Mavenclad[®] and must agree to continue to practice adequate contraception for at least 6 months after the last dose (see [Appendix 12: Birth control methods which may be considered as highly effective](#)). A woman is considered of child-bearing potential (WOCBP), i.e. fertile, following menarche and until becoming post-menopausal unless permanently sterile. Women using systemically acting hormonal contraceptives should add a barrier method during Mavenclad[®] treatment and for at least 4 weeks after the last dose in each treatment year.
6. WOCBP must not be pregnant nor lactating or breast-feeding at Screening through at least 1 week after the last dose
7. Male subjects must be willing to use a condom in addition to having their female partner use another form of contraception (such as an intra-uterine device [IUD], barrier method with spermicide, or hormonal contraceptive [e.g., implant, injectable, patch or oral]) from Baseline until 6 months after the last dose of Mavenclad[®], unless their partners are infertile or surgically sterile.
8. Subjects who test positive for Varicella Zoster virus (VZV) will be included. In case of negative serology, the subject may be included after 4 to 6 weeks of receiving VZV vaccination.

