This will be an open-label, single-arm, multicenter, 2-year Phase IV trial. Subjects meeting the eligibility criteria during a pre-baseline screening period of up to -3 months before baseline (Day 1 of treatment) will receive an initial treatment course in Year 1 and a retreatment course in Year 2.

Subjects will attend visits for assessments at end of Months 1,2,3,6, 12 following Baseline (Day 1 of treatment) and at end of Month 15,18, 24 following second treatment course (Month 1 of Year 2), respectively. Subjects will attend visits for blood sample as per mandatory monitoring at pre-Baseline and at Months 2, 6, 12, 14, 18 and 24. The primary endpoint(s) will be assessed during the first 6 months, secondary and tertiary endpoints will be assessed up to Month 24.

CCI [REDACTED]

Visit schedules for efficacy and safety assessments are detailed in the Schedule of Assessments.

Planned number of subjects: Approximately 265 subjects are planned to be included

Primary endpoint(s):

- Differences in the counts of combined unique active (CUA) MRI lesions during the first 6 months (i.e. during periods months 1-6, 2-6, 3-6) compared to baseline (i.e. the period screening to baseline)

Secondary endpoints:

- Characterization of immune cell subsets count at the end of 3, 6, 12, 15, 18 and 24 months compared to baseline

Tertiary endpoints:

Safety:

- Occurrences of treatment-emergent adverse events (TEAEs) and serious adverse events (SAEs) including and up to 24 months

Clinical:

- Changes in Symbol Digit Modality Test (SDMT) outcome at the end of 6, 12, 18 and 24 months compared to baseline
- Disability evolution as measured by Expanded Disability Status Scale (EDSS)/ Kurtzke Functional System (KFS), 9-Hole Peg Test (9HPT), Timed 25-Foot Walk (T25FW) at the end of 6, 12, 18 and 24 months compared to baseline
- Annualized Relapse Rate (ARR) between baseline and 24 months
- Changes in CUA lesions during the following post-baseline periods –compared to baseline period (i.e. the period from screening to baseline):
 - Period of month 6 to month 12
 - Period of month 1 to month 12
 - Period of month 18 to month 24
 - Period of month 1 to month 24Further periods and comparisons may be defined in the SAP
- Number of CUA lesions during the baseline and post-baseline periods as defined above
- Changes in active T1 gadolinium (Gd)+ lesion count at the end of 1, 2, 3, 6, 12, 15, 18 and 24 months compared to baseline

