7.1 Schedule of Assessments

7.1.1 Pre-Baseline Screening (-3 months)

During the pre-Baseline screening visit, the prospective subject will be informed of the trial objectives and overall requirements, and written informed consent will be obtained prior to any trial specific assessments (see Section 9.2). The subject will then undergo a clinical MRI assessment centrally for disease activity and also to rule out PML. The read-out of this MRI scan to ensure compliance with the inclusion and exclusion criteria will be at investigator discretion (see Section 5.3).

A complete Screening Evaluation is to be performed during 3 months from Baseline, which will include the following assessments:

- Signing informed consent form
- Register IRT for shipment of medication to the site
- Demographic data, including date of birth, gender and race
- Medical history
- Disease history, including classification of disease, number of relapses within the past 12 months, treatment history, diagnosis date
- Review of inclusion/exclusion criteria
- Physical examination, including vital signs (including blood pressure, heart rate, temperature), height and weight
- Serology (HIV, Hepatitis C and B, and Varicella Zoster virus) and TB test
- MRI assessment (see Section 7.3.1)
- Neurological assessment including EDSS/KFS, 9HPT and T25FW (excluding SDMT) (see Section 7.3.2)
- The contraceptive method used will be recorded, or, alternatively, if applicable, the age at menopause will be documented
- Blood samples for safety analysis at local laboratory (see Section 7.4.3)*.
- Urine pregnancy test (for female subjects of child-bearing potential only) at local laboratory**
- Assessment of AEs, concomitant medications and concomitant procedures

*** If the local laboratory blood at the Screening visit is conducted within 10 days of Study Day 1, no blood samples need to be repeated at Study Day 1.**

****Additional serum or urine pregnancy tests will be permitted throughout the trial period as required by country specific regulations.**

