1. H_{03}
2. H_{02}
3. H_{01}

The 3 hypotheses will be tested one-sided on a 2.5% significance level. The testing procedure will stop as soon as one of the hypotheses cannot be rejected following the pre-specified order. Due to this sequential order of tests an adjustment for a potential type-I-error due inflation due to the multiple testing is not required.

An estimate for the difference in CUA lesions during the specified periods compared to the baseline period will be reported, together with one-sided p-values. In addition, 95% CI and two-sided p-values will be presented to allow for comparison with the two-sided secondary and tertiary analyses.

Robustness Analyses

The robustness of the primary analysis model will be evaluated by repeating the analysis using generalized model assuming a negative binomial distribution.

In order to evaluate the robustness of the assumption that missing data are observed at random (MAR), the primary analysis will be repeated applying a pattern mixture model. If missingness can be considered MAR (e.g. MRI missing for technical reasons), data will be imputed by multiple imputation from post-baseline data while if considered not missing at random (MNAR) (e.g., drop-out due to lack of efficacy), data will be imputed from baseline data. The propensity score method based on CUA lesion count during the baseline period, age, and EDSS will be applied.

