The last non-missing measurement prior to start of study medication will serve as the Baseline measurement. Measurements performed on the day of first intake of study medication are assumed to be “prior to start of study medication”, as long as it has not been confirmed that the procedure was performed afterwards. This assumption is justified as following the sequence of procedures as specified in the study protocol. The intake of study medication should be the last procedure on the Visit day.

The MRI scans will be reconciled during central MRI review process. Therefore, MRIs will be considered as Baseline MRIs if assigned to the Baseline Visit by the central imaging review.

Definition of Study Periods

- Baseline Period: The Baseline Period is defined as the Period between the Screening and the Baseline MRI scan.
- Post-Baseline Period: The post-Baseline Periods that are used in the primary analysis are defined as follows:
 - Period 1 (p₁) is defined as the Period between Month 1 and Month 6 MRI scans.
 - Period 2 (p₂) is defined as the Period between Month 2 and Month 6 MRI scans
 - Period 3 (p₃) is defined as the Period between Month 3 and Month 6 MRI scans

In addition, the following post-Baseline Periods are defined solely for tertiary analyses:

Three months Periods

- Period 3.1 (p_{3.1}) is defined as the Period between Baseline and Month 3 MRI scans.

Six months Periods

- Period 6.1 (p_{6.1}) is defined as the Period between Baseline and Month 6 MRI scans,
- Period 6.2 (p_{6.2}) is defined as the Period between Month 6 to Month 12 MRI scans,
- Period 6.3 (p_{6.3}) is defined as the Period between Month 12 to Month 18 MRI scans,
- Period 6.4 (p_{6.4}) is defined as the Period between Month 18 to Month 24 MRI scans.

Periods excluding the Period between the Baseline scan and the Month 1 MRI scan:

- Period 11.1 (p_{11.1}) is defined as the Period between Month 1 to Month 12 MRI scans,
- Period 11.2 (p_{11.2}) is defined as the Period between Month 1 to Month 24 MRI scans.

Yearly Periods:

- Period 12.1 (p_{12.1}) is defined as the Period between Baseline to Month 12 MRI scans,
- Period 12.2 (p_{12.2}) is defined as the Period between Month 12 to Month 24 MRI scans.

2 -Year Period:

- Period 24.1 (p_{24.1}) is defined as the Period between Baseline to Month 24 MRI scans.

Sequential Visit Periods

- Period 100.0 (p_{100.0}) is defined as the Period between Screening and Baseline (equivalent to Baseline Period) MRI scans

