All derived lesion counts (except for the Mean T1 Gd+ lesion count) as specified below will be classified as NE if one of the components required for the calculation has been classified as NE by the central reading. The Mean T1 Gd+ lesion count will be set to NE only, if all T1 Gd+ lesion counts that correspond to the respective Period are classified as NE. In all other cases the mean will be calculated based on the available counts during the respective Period.

T1 Gd+ lesion count

As with this procedure a Visit is assessed multiple times for the T1 Gd+ and thus T1 Gd+ will be reported multiple times per Visit, the value for a Visit of the earliest available Period will

be selected for the statistical analysis. As the Global Review will ensure that all duplicates have identical lesion count, this rule does not have an impact on the number of T1 Gd+ but defines further attributes (e.g. date of review).

The T1 Gd+ counts for a Period will be defined as the sum of the T1 Gd+ lesions from all scheduled MRI scans reported for a Visit that is included in a Period divided by the actual number of MRI scans with a reported lesion count (i.e. not NE) during a Period.

- T1 Gd+ lesion count (by Visit) = T1 Gd+ lesions count from the MRI at the respective Visit
- Mean T1 Gd+ lesion count (by Period) = T1 Gd+ lesion count during the Period / # of scans belonging to the respective Period with non-missing T1 Gd+ lesion count.

MRIs are assigned to a Period as follows:

- Baseline Period:
 - Screening Visit
 - Baseline Visit
- Period 1:
 - Month 1 Visit
 - Month 2 Visit
 - Month 3 Visit
 - Month 6 Visit
- Period 2:
 - Month 2 Visit
 - Month 3 Visit
 - Month 6 Visit
- Period 3:
 - Month 3 Visit
 - Month 6 Visit

Active T2 lesion count

As the new or enlarging T2 lesion count depends on the length of the Period, it will be presented as reported (non-standardized) and standardized to 1 months (30.4375 days):

- Period length (days) = MRI date at end of Period – MRI date at start of Period +1,
- Standardized total T2 lesion count (by Period per 1 months) = Total number of T2 lesions per Period * 30.4375 / Period length.

The following types of T2 lesions are defined per Period (standardized and non-standardized):

- Total new T2 lesion count =
Total number of new T2 lesions with T1 Gd+
+ Total number of new T2 lesions without T1 Gd+
- Total enlarging T2 lesion count =
Total number of enlarging T2 lesions with T1 Gd+
+ Total number of enlarging T2 lesions without T1 Gd+,

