14.1.1 Primary Objective: Analysis of primary endpoints

The differences in counts of CUA lesions will be evaluated using a mixed-effects linear model, accounting for within-center/region correlation through a hierarchical model. The analysis will adjust for Baseline factors deemed to be prognostic for the primary endpoint, as judged by clinical experts:

- CUA lesion count during the Baseline Period,
- Age,
- EDSS at Baseline ($\leq 3 / > 3$).

The results of the mixed-effects linear model will be used to describe the effect size. A review of Baseline data has shown that the distribution of the primary endpoint data does not follow Normal distribution. Consequently, the hypotheses will be tested by a Wilcoxon signed-rank test which employs ranks of absolute differences from Baseline for each testing Period (i.e., p_1 , p_2 , and p_3) using average ranks for tied values.

The analysis will also adjust for the difference in length and number of MRIs of the Periods to be compared (see Section 9 “Data Handling of MRI data” for details of lesion count standardization).

The difference in the counts of CUA lesions during the three Periods compared to the Baseline Period will be tested in a sequential order. The three hypotheses are defined as follows:

$$H_{0i}: \Delta \text{CUA}(p_i) \geq 0 \quad \text{vs.} \quad \Delta \text{CUA}(p_i) < 0, \quad i = 1, 2, 3$$
$$\Leftrightarrow H_{0i}: \#\text{CUA}(p_i) \geq \#\text{CUA}(p_0) \text{ vs. } \#\text{CUA}(p_i) < \#\text{CUA}(p_0), \quad i = 1, 2, 3$$

with

$$\Delta \text{CUA}(p_i) = \#\text{CUA}(p_i) - \#\text{CUA}(p_0), \quad i = 1, 2, 3,$$

$$\#\text{CUA}(p_i): \text{standardized CUA lesion count during Period } p_i, \quad i = 0, 1, 2, 3,$$

p_0 : Baseline Period (Period from Screening to Baseline),

p_i : Period Month i to Month 6, $i = 1, 2, 3$.

The sequential testing procedure will start with Period p_3 , followed by Period p_2 and p_1 , i.e., the hypotheses will be tested in the following order:

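### For subjects who enter only through a T1 Gd+ lesion on the Screening MRI, the same scan makes up half of the Gd+ part of the primary comparator, and no CUA analysis leaves it out

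*Protocol*

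**What the plan says.** - **Design.** Protocol 5.2: "This will be an open-label, single-arm, multicenter, 2-year Phase IV trial". Each subject's own pre-treatment period is the only comparator.
- **Entry.** Protocol 5.3.1, criterion 3, has two routes. The first, for subjects on a DMD, is "One relapse in the previous year and at least 1 T1 Gd+ lesion or 9 or more T2 lesions". The second is two or more relapses and has no MRI condition.
- **Use of the Screening scan.** Protocol 7.1.1: "The read-out of this MRI scan to ensure compliance with the inclusion and exclusion criteria will be at investigator discretion".
- **Comparator.** SAP Section 9: "The Baseline Period is defined as the Period between the Screening and the Baseline MRI scan". On the Gd+ part: "The T1 Gd+ counts for a Period will be defined as the sum of the T1 Gd+ lesions from all scheduled MRI scans", divided by the number of scans with a reported count. For the Baseline Period these are the Screening and Baseline Visit scans. CUA is this mean plus the monthly count of active T2 lesions without Gd+. That T2 count is calculated only if Gd+ is available at both ends of the Period, so the Screening scan always has weight 1/2 in the Gd+ part of #CUA(p0).
- **Test.** SAP 14.1.1: "the hypotheses will be tested by a Wilcoxon signed-rank test which employs ranks of absolute differences from Baseline for each testing Period". The level is in Protocol 8.5.2: "The 3 hypotheses will be tested one-sided on a 2.5% significance level".

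**The concern.** A count that had to be at least 1 for a subject to enter will on average be lower at the next scan, even if the underlying disease is unchanged. When the qualifying scan also enters the comparator, this fall is read as treatment effect. A single-arm trial has no control group in which the same fall would appear. The signed-rank test is unadjusted, and adjusting the mixed model for Baseline CUA does not remove a shift in the group mean. The analyses in SAP 14.1.2 change the model, the imputation, the categories or the subjects, but all keep the same p0. The subset with Baseline Period CUA above 0 selects again on the comparator itself. At stake is whether a one-sided p-value below 2.5% can be read as evidence of onset of action.

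**Working it through.** **Inputs from the documents.** Planned N is 265 (Protocol synopsis: "Approximately 265 subjects are planned to be included"). The test is a one-sided signed-rank test at 2.5%, Screening has weight 1/2 in the Gd+ part, and the Screening-to-Baseline MRI gap is from 4 weeks to about 3 months. The assumptions behind N are blacked out, so N cannot be reproduced. For scale only, the mean shift detectable with 80% power is (1.960 + 0.842)/√265 = 0.172 SD.

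**Assumptions, not in the documents.** Lesion activity is stable and there is no drug effect. Gd+ counts are gamma-Poisson with mean m = 1 per scan and shape k = 0.5. The monthly T2 rate is half the Gd+ rate. No scans are missing. The eligibility read equals the central read. q is the share of subjects who enter only through Gd+ of at least 1 on the Screening scan.

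**Step 1: excess per selected subject.** Let λ be the subject's own Gd+ rate and Y the Screening count.
- P(Y≥1) = 1 − (1 + m/k)^(−k) = 1 − 3^(−0.5) = 0.423
- E[λe^(−λ)] = m/(1 + m/k)^(k+1) = 1/3^1.5 = 0.192
- Excess in the Screening count = 0.192/0.423 = 0.455. With weight 1/2, the excess in p0 is 0.23 CUA units.
- With k = 0.5 and m = 0.5 or 1.5, the same formula gives 0.30 and 0.19.

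**Step 2: effect on the group mean.** Unselected subjects have expected CUA of 1 + 0.5 = 1.5. Selected subjects have mean rate (1 − 0.192)/0.423 = 1.91, so their expected p0 is 1.5 × 1.91 + 0.23 = 3.09.
- q=10%: shift 0.023, p0 0.9 × 1.5 + 0.1 × 3.09 = 1.66, a fall of 1.4%
- q=25%: shift 0.057, p0 1.90, a fall of 3.0%
- q=50%: shift 0.114, p0 2.30, a fall of 5.0%

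In simulation at q=20% the shift is about 0.035 SD, well below 0.172 SD.

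**Step 3: false rejection of H03.** Separate simulations with m = 1, k = 0.5 and gaps of 1 to 3 months give about 2-3% at q=0, 3-4% at 5%, 4-6% at 10%, 10-17% at 25% and 29-40% at 50%. A check run for this write-up (2,000 trials per cell) gave:

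| q | gap 1 month | gap 2 months | gap 3 months | Gd+ from Baseline scan only, all gaps |
|---|---|---|---|---|
| 0 | 1.0% | 2.2% | 2.5% | 1.0-1.2% |
| 5% | 2.6% | 3.8% | 3.5% | 1.0-1.4% |
| 10% | 3.2% | 5.4% | 5.8% | 1.0-1.4% |
| 25% | 8.6% | 13.6% | 14.2% | 0.8-1.2% |
| 50% | 28.8% | 38.8% | 39.2% | 1.0% |

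Rejection rises with q at every gap. At one month it starts from about 1% and stays at or below the low end of the ranges. If the T2 rate equals the Gd+ rate, the one-month figures fall to 2.2%, 5.6% and 17.8% at q=10%, 25% and 50%. For the Mean T1 Gd+ contrast of SAP 14.3.3, rejection is about 16% at q=25% and 45% at q=50%.

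**Step 4: other activity levels.** At a 2-month gap, with m from 0.5 to 1.5 and shape 0.3 to 1.0 (shape varied only at m = 1), H03 rejection is 4.9-10.2% at q=10%, 6.5-21.8% at 20% and 22.0-76.9% at 50%.

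**Step 5: negative control.** A one-sided signed-rank test of the Screening-to-Baseline Gd+ change is significant in about 7-9% of runs at q=10%, 25-30% at 25% and 70% at 50%. It detects a large q but has little power for a small one.

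**The case against.** **The SAP already has partial checks.** SAP 14.3.3 plans the change in Gd+ by Visit from the Baseline scan alone. SAP 14.1.2 repeats the primary analysis by High-relapse activity, and HRA subjects have at least two relapses and so did not need the MRI route. Both stand. But the first covers Gd+ and not CUA, and the second is not presented as a check on this bias. SAP 11.3 tabulates Screening and Baseline Gd+ without comparing them. HRA is also not perfectly clean: its look-back is 396 days before Baseline, and a relapse after Screening counts.

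**q may be small.** Subjects with 9 or more T2 lesions, or with two or more relapses, enter whatever their Gd+ count. Nothing in the documents supports a q of 25-50%. This stands, and it is why only a range can be given.

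**The scan link is assumed.** Criterion 3 does not say which scan must show the lesion. Eligibility is read at the investigator's discretion, while the endpoint uses the central read. With an assumed 80% lesion agreement and some local false positives, at a 3-month gap, H03 rejection falls from about 17% to 12% at q=25% and from 42% to 27% at q=50%.

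**There may be an opposite force.** The first route requires a DMD, and other DMDs are prohibited during the trial (Protocol 6.5.2). If post-Baseline activity rose by an assumed 10% after a DMD is stopped, H03 rejection would be 0.1% at q=20% and 0.4% at q=50%.

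These points limit the size. They do not remove the overlap between entry and comparator.

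**Conclusion.** The overlap is real and its direction is known: it favours a fall from p0. Its size cannot be fixed from the documents. If q is 5-10%, the one-sided error is about 3-6% instead of 2.5% under the central assumptions. It becomes serious only if a quarter or more of the subjects enter solely through a Screening Gd+ lesion. These figures rest on stable activity, a lesion seen on the Screening scan, and agreement between the two reads. 

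A reader might infer that p0 is inflated for every subject with a Gd+ lesion, or that a positive primary result would be an artefact. The documents do not support either. Selection acts only on those who would otherwise have failed criterion 3, only the Gd+ part of CUA is directly selected, and the spurious fall in mean CUA is about 1-5% in the worked case. A large observed fall could not come from this mechanism. A small or borderline one could, and the planned CUA analyses would not show the difference.

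**What to change.** In SAP 14.1.2:

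1. Add a sensitivity analysis of H03, H02 and H01, and of the Mean T1 Gd+ contrasts of 14.3.3, with the Gd+ part of the Baseline Period value taken from the Baseline Visit scan only.
2. Report the paired Screening-to-Baseline change in Gd+ with a signed-rank test, an estimate and a confidence interval, as a negative control. Because its power is low when q is small, a non-significant result should not be read as absence of bias.
3. Designate the HRA subgroup result as a further check on this bias.

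SAP Section 7 records decisions taken after the primary analysis, so anything added now should be labelled post hoc, as SAP Section 4 provides. The results should inform the reading of the primary analysis. Making them a condition for concluding onset of action would change the decision rule after the fact.

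The cost is SAP wording and a few outputs from data already collected. A one-scan Gd+ baseline is noisier, and the test then runs at about 1%, below its nominal level. Two limits remain. The fix does not remove regression to the mean from selection on recent relapses. And because the criteria are reviewed again at Baseline (Protocol 7.1.3), it should be confirmed that the Baseline scan was not itself used to qualify subjects.
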